Intravenous fluid therapy for the treatment of emergency department patients with migraine headache: a pilot randomized controlled trial

Abstract:

Headache is one of the most common reasons patients visit the emergency department (ED), with migraines accounting for over one million annual US ED visits. While intravenous fluid (IVF) has not been prospectively studied in migraine patients, there is evidence that intravascular volume status affects central pain processing, and dehydration can trigger migraines. We propose a pilot, randomized controlled trial assessing the impact of an IVF bolus on patients with migraine headache. We hypothesize that patients who receive IVF will experience greater improvement in pain one hour after treatment as compared to controls. Adults treated in the Cooper ED with migraine headache will be randomized to receive normal saline at either 1000 ml/hr (treatment) or 10 ml/hr (control) for one hour, with a comparison in pain scores before and after treatment. Our first specific aim will establish the feasibility of successfully enrolling patients with migraine in the study and adhering to the study protocol. Our second specific aim will examine the efficacy of a normal saline bolus for relieving pain among patients with migraine headache. The data collected during this pilot study will support a competitive, larger-scale external grant application further investigating the efficacy of IVF for migraine.

Research plan

I. Project statement

Patients commonly present to the emergency department due to migraine headache. While some patients receive intravenous fluids as a method of controlling pain, the effectiveness of this intervention has not been prospectively studied. Our long-term objective is to determine the effect of an intravenous fluid bolus on pain among patients treated in the emergency department for migraine headache. The purpose of this pilot study is to obtain feasibility and preliminary outcome data in support of a future trial.

II. Specific aims

Migraine headache exacerbation is one of the most common reasons that people seek emergency department (ED) care.¹ Common treatments in the emergency department include phenothiazines,² serotonin receptor agonists,³ and corticosteroids.⁴ Because severe headache exacerbation is often refractory to these interventions, approximately 50% also end up receiving opioids,^{5, 6} despite the fact that these medications are contraindicated in migraine headache, can cause headache recurrence, and can contribute to drug abuse and addiction.⁷⁻¹¹

One commonly used but little-studied treatment for migraine headache is IV fluid (IVF). Using a nationally representative staged probability sampling survey we recently found that approximately 40% of patients treated in US EDs for headache received IV fluid therapy. Theoretical reasons to suggest that IVF may be useful in painful conditions such as migraine headache include data from healthy volunteers suggesting that IV fluid administration may reduce headache pain by correcting dehydration, and by reducing pain-related brain activity in the anterior cingulate cortex, insula, and thalamus. However, despite its common use, no prospective studies have been performed evaluating the efficacy of IVF in acute migraine headache exacerbation. Consistent with contemporary uncertainty regarding efficacy, our national survey data indicate that the use of IVF is highly variable across institutions. If IVF is efficacious, then currently it is a highly underutilized opioid-sparing intervention. In contrast, if IVF is not efficacious, then IVF treatment currently adds unnecessary cost, resource utilization, and time to contemporary ED care.

Our study coordinator and network of ED-based research associates currently screen and enroll patients for research studies in the Cooper Hospital ED 14 hours per day, 7 days per week. We will use this research infrastructure to recruit patients (n = 50) presenting to the ED with a chief complaint of headache or migraine who meet International Classification of Headache Disorders-3 (ICHD-3) diagnostic criteria for migraine. As described below, individuals with extensive vomiting or other definitive IVF requirement will be excluded. Patients will be randomized to receive a 1000 ml bolus of normal saline over one hour vs. normal saline at 10 ml/hr for one hour, and pain, functional status, and side effects will be assessed at time zero, one hour, two hours and 48 hours.

Hypothesis 1: The proposed RCT protocol is feasible. Specific Aims

- **1a.** To determine whether the proposed study protocol can successfully recruit at least 75% of eligible patients.
- **1b.** To assess the ability of the proposed protocol to successfully blind participants to their intervention group, such that fewer than half of participants correctly identify their treatment arm.
- **1c**. To test the ability of the proposed protocol to successfully obtain patient follow-up at one hour, two hours, and 48 hours in at least 85% of participants.

Hypothesis 2: IVF administration will result in reduced pain scores in the ED and at follow-up. Specific Aims

1a. To test the efficacy of IVF in achieving an improvement in reported pain (0-10 scale) of at least 1.3 (minimally significant pain difference) as compared to controls between time 0 and one hour.

The proposed study constitutes a critical first step in demonstrating the potential feasibility and value of performing a large-scale RCT evaluating the potential efficacy of IVF administration for individuals presenting to the ED with migraine headache. This study will collect the necessary data to advance to initial stage NIH (R03, R21, R34) or PCORI funding.

III. Research strategy

A) Significance

Headache is a substantial global public health problem,²⁰ and the fourth most common reason that patients visit an emergency department (ED) in the United States (US). Migraine headache accounts for over one million patients encounters in US EDs each year, and many more patients seek care for migraine-like headaches.⁵ While multiple drugs are currently used in the management of migraine exacerbations, including non-steroidal anti-inflammatories, phenothiazines, serotonin receptor agonists,³ and corticosteroids,⁴ severe headaches are often refractory to these interventions. As a result, approximately 50% of ED patients with migraine headache receive opioids. 5, 6 Furthermore, ED opioid use for headache has increased over time. ²¹ This is despite known risks of opioid use in patients with migraine headache, including the development of transformed migraine, in which patients with infrequent migraine symptoms develop increasingly chronic, frequent, and disabling headaches, 7, 11 as well as opioid-related antagonism of other analgesic medications such as COX1/COX2 inhibitors.9 Additionally, chronic opioid use and abuse is an enormous public health problem in the United States, ²² with opioid-related overdose deaths increasing 200% since 2000. 10 Importantly, initiation of opioid medications for acute pain in the ED among opioid-naïve patients is associated with increased risk of ongoing use one year later.8 The high rate of opioid utilization for migraine headache despite these known risks indicates the need to development effective, opioid-sparing interventions.

Data from both healthy volunteers and from other painful conditions suggest that fluid administration may provide effective analgesia for patients with migraine. Even mild dehydration lowers pain thresholds, and increases central pain-related activity in the anterior cingulate cortex, insula, and thalamus. ¹⁶⁻¹⁸ Consistent with this hypothesis, headache is commonly reported by patients undergoing dialysis, ²³ and recent research has identified dehydration as a trigger for migraine headache. ¹³⁻¹⁵

Despite these theoretical benefits, IVF has not been prospectively studied in patients with migraine and its efficacy is unknown. One recent secondary analysis of data from four ED-based migraine headache trials evaluating the use of metoclopramide demonstrated no association between IVF administration and improved pain outcomes, though the observational nature of these data are subject to substantial confounding. Despite this lack of existing clinical evidence, experts often recommend IVF for patients requiring ED treatment for migraine, ^{25, 26} and approximately 40% of patients visiting US EDs for headache receive treatment with IVF. ¹² If IVF is beneficial, then this represents a substantial opportunity to improve the care of patients with this common, painful condition through increased use of this potentially opioid-sparing intervention. If, however, IVF does not benefit individuals with migraine, then these patients are burdened by unnecessary costs. In addition, while generally safe, risks associated with IV placement and/or fluid administration include pain with insertion, ²⁷ infection, ²⁸ and thrombophlebitis. ²⁹ While these outcomes are rare, the use of IVF in millions of headache patients each year makes them relevant to risk/benefit calculations. If found to be ineffective, IVF may also contribute to ED crowding by unnecessarily prolonging ED length of stay, and by occupying staff time when this time is often critical to ensuring patient safety.

B) Innovation

The proposed study will be the first randomized trial assessing the efficacy of IVF in migraine headache, thereby addressing a significant knowledge gap in the treatment of this common disorder. Additionally, we plan to assess the success of our blinding strategy. Several prior studies assessing the effectiveness of IVF for the treatment of other painful conditions have attempted to achieve blinding by placing opaque covers over the IV bag and IV pump.^{30, 31} However, these studies have not assessed the success of this blinding method. Validation of this technique has the potential to inform the design of future studies of IVF across a broad spectrum of clinical conditions.

C. Approach

We intend to perform a small-scale pilot study assessing the effectiveness of IVF therapy for patients presenting to the ED with migraine headache.

1. Study participants

Participants will be English-speaking patients aged 18 or older, treated in the Cooper Hospital ED with a headache meeting ICHD-3 criteria for migraine. Patients will be excluded if in the opinion of the treating physician IVF administration is definitively indicated (ie. intractable vomiting, severe dehydration) or contraindicated (e.g. exacerbation of congestive heart failure).

Research assistants who are trained to identify potential clinical study participants and assess their eligibility for study enrollment are available in the ED from 8:30 am until 10:30 pm, 7 days per week to screen patients for inclusion.

2. Interventions

No previous trials have prospectively studied an IVF bolus for adults with migraine, limiting data on which to make dosing decisions. However, several trials have assessed the impact of IVF on postoperative nausea and vomiting and post-operative opioid requirements. One compared 15 ml/kg (mean total intervention dose of 1215 ml) with 2 ml/kg (mean dose 226 ml) of crystalloid solution before induction of anesthesia for minor surgery, finding a substantial reduction in post-operative nausea and vomiting, along with trends toward lower post-operative opioid requirements.³² Two additional small trials showed that for patients undergoing gynecologic procedures a 1000 ml crystalloid bolus resulted in improved post-operative nausea and vomiting compared with controls.^{33, 34} Finally, another trial comparing a control group of 2 ml/kg crystalloid to 12 ml/kg crystalloid solution or 12 ml/kg colloid solution showed improved post-operative nausea and vomiting among the two experimental arms. 35 In addition to these results showing efficacy with doses of approximately 1000 ml, clinical experience suggests that a dose of 1000 ml is commonly selected by ED physicians when treating patients with migraine, making this dose relevant to current clinical practice. Finally, a dose of 1000 ml limits opportunities for unblinding by avoiding administration of more than one bag of IVF. Based on these considerations, we plan to study the efficacy of a 1000 ml normal saline bolus versus control. In order to maximize the generalizability of our results, we will not restrict the use of additional interventions by ED providers.

Patients will be randomly allocated between two arms:

Patients in the intervention arm ("IVF group") will have a peripheral IV line placed by ED staff, and will receive 1000 ml of 0.9% normal saline bolus over one hour.

Patients in the control arm ("control group") will have a peripheral IV line placed by ED staff, and will have a 1000 ml bag of 0.9% normal saline attached to the IV line, but the IV pump will be programmed to infuse 10 ml of fluid over one hour.

3. Allocation and blinding

We will randomize patients in permuted blocks of 4 or 6. Study assignments will be made through the use of sequentially numbered, opaque, sealed envelopes. Following enrollment, the nurse -- who will remain un-blinded -- will open the envelope and initiate the assigned intervention. An opaque cover will be placed over the IV pump, fluid bag, and drip chamber to maintain blinding of the patient, treating physician, and outcome assessor. Following completion of the intervention, in order to evaluate the success of blinding, patients and outcome assessors will be asked which treatment group they think was assigned.

4. Data collection

Research assistants will collect demographic information from patients, including age, sex, race, ethnicity, pre-existing comorbid conditions, and headache history.

We will assess pain at time 0 (start of the intervention), one hour (end of the intervention), and two hours using both a categorical scale (none, mild, moderate, or severe) and an 11 point verbal pain scale ranging from 0 (no pain) to 10 (worst pain imaginable), which has been validated for use in the ED setting.³⁶

Functional disability will be assessed before treatment, at one hour, and two hours. As recommended by the International Headache Society,³⁷ patients will describe their functional disability due to headache as none, mild (able to perform all activities of daily living, but with some difficulty), moderate (unable to perform some activities of daily living), and severe (unable to perform most activities or requiring bed rest).

We will measure adverse effects of treatment, including pain at the IV site by asking participants to rate the pain associated with IV insertion, as well as IV site pain at one and two hours.

Research assistants will record visit characteristics, including the timing of medications administered, need for rescue medication, opioid use, length of stay in the ED, and ED disposition (discharged, observation, admission).

Research assistants will contact participants 48 hours after they leave the ED. It is anticipated that the substantial majority of patients will have been discharged from the hospital, in which case

follow-up will occur over the telephone. During this follow up assessment we will ask participants about their current pain, any recurrence of pain since leaving the hospital, current functional status, ability to tolerate oral intake, and adverse effects potentially related to the study intervention, including pain at the IV site, symptoms of thrombophlebitis, or peripheral edema. Global assessment of treatment is a function of both efficacy and tolerability, and will also be assessed by asking patients "The next time you visit the ED with a headache, would you wish to receive the same IV fluid treatment again?"

5. Outcomes

The primary outcome will be the difference in pain rating (0-10) between the start of the study intervention and one hour later, at completion of the intervention. The minimum clinically significant difference between treatment groups on the 0-10 verbal scale is 1.3. 36, 38, 39

Secondary outcomes will include:

Percentage of patients in each group who are pain-free two hours after initiation of the study intervention. This outcome is recommended for study by the International Headache Society.³⁷

Difference in verbal pain scale between start and two hours.

Global assessment of treatment, as described above.

Functional disability at one and two hours as compared to the start of treatment.

6. Analysis

We performed our sample size calculation with the understanding that the primary goal of this pilot study is to demonstrate the feasibility of the study protocol so as to inform a subsequent larger-scale trial.⁴⁰ The sample size calculation assumes a normal distribution. A sample size of 50 patients will provide the ability to detect a protocol adherence rate of 85% (+/- 10%) at a confidence level of 95%. In 2015, the Cooper ED treated over 300 patients who were diagnosed with migraine headache, suggesting that a goal of 50 participants over the 10 month active-enrollment period is attainable.

Using an intention-to-treat analysis, the primary outcome will be analyzed by calculating the mean change in pain scale within each study group, as well as 95% confidence intervals surrounding these point estimates.

IV. Expected outcome

We anticipate that the results from this study will demonstrate the feasibility of identifying and enrolling ED patients with migraine headache, completing the study protocol, and obtaining outcome data including post-discharge follow-up assessments. We will determine the success of blinding both participants and outcome assessors to the study intervention. This study will also provide preliminary

outcome data regarding the use of an IVF bolus for the treatment of migraine headache. These pilot data will be used to support a future grant application for a larger study which will be appropriately powered to determine the efficacy of this intervention.

References

- 3. Bird S, Derry S and Moore RA. Zolmitriptan for acute migraine attacks in adults. *Cochrane Database Syst Rev.* 2014; 5: CD008616.
- 4. Singh A, Alter HJ and Zaia B. Does the addition of dexamethasone to standard therapy for acute migraine headache decrease the incidence of recurrent headache for patients treated in the emergency department? A meta-analysis and systematic review of the literature. *Acad Emerg Med.* 2008; 15: 1223-33.
- 8. Hoppe JA, Kim H and Heard K. Association of emergency department opioid initiation with recurrent opioid use. *Ann Emerg Med.* 2015; 65: 493-9 e4.

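### Aim 1b sets its blinding pass mark at the chance value for two arms, so with a forced guess perfect blinding fails it 50% to 56% of the time

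*Combined protocol and SAP*

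**What the plan says.** Aim 1b is one of three feasibility aims under Hypothesis 1. It defines successful blinding of participants by a numerical threshold: "such that fewer than half of participants correctly identify their treatment arm".

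The design has two arms (III.C.2 Interventions: "Patients will be randomly allocated between two arms") and plans for 50 participants. The allocation ratio is not stated, but the block sizes are even (III.C.3: "We will randomize patients in permuted blocks of 4 or 6"). After the intervention, "patients and outcome assessors will be asked which treatment group they think was assigned" (III.C.3 Allocation and blinding). The text does not say whether a guess is required, whether don't-know is an option, or who is in the denominator.

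The analysis section (III.C.6) has no analysis of the blinding data: no chance reference, interval, test or blinding index. Section IV nevertheless promises a verdict for two groups: "We will determine the success of blinding both participants and outcome assessors to the study intervention". Section III.B presents the check as an innovation, saying "Validation of this technique has the potential to inform the design of future studies of IVF across a broad spectrum of clinical conditions".

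**The concern.** With two arms, a participant who knows nothing and must guess is right half the time. A result of 50% correct is what a perfect cover would be expected to produce, yet Aim 1b counts exactly 25 of 50 as a failure. The pass mark sits at the ideal value, and chance alone decides on which side of it a well-blinded trial falls.

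Feasibility is the pilot's stated primary goal, and the blinding check is meant to validate the opaque cover for other fluid trials. Under a forced guess, a cover that works perfectly is about as likely as not to be reported as failing. Under a different answer format the same sentence errs in the other direction. The verdict then depends on a choice that the plan does not make.

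**Working it through.** **Inputs from the plan.** Two arms (III.C.2); n = 50 (II. Specific aims); pass only if the share correct is below one half (Aim 1b).

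**Assumptions.** 1:1 allocation; independent, even, forced guesses, so that the probability of a correct guess under perfect blinding is p = 0.50. With even guesses p is 0.50 at any allocation ratio.

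**The plan's own figure.** The only calculation given is the sample size for 85% adherence to within 10 points at 95% confidence. It reproduces: n = 1.96² × 0.85 × 0.15 / 0.10² = 48.98, so 49, and the half-width at n = 50 is 1.96 × √(0.85 × 0.15 / 50) = 0.099. It does not bear on Aim 1b, for which there is no calculation.

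**Step 1: the rule under perfect blinding.** Let X be the number correct, X ~ Binomial(50, 0.5). The rule passes if X ≤ 24.

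- P(X ≤ 24) = 0.444, so the probability of false failure is 1 − 0.444 = 0.556.
- For any odd number of answers (for example 49, 45 or 43) the distribution is symmetric with no middle value, so false failure is exactly 0.500.
- For even numbers from 42 to 48 it is 0.561 down to 0.557.

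**Step 2: the rule under real unblinding** (n = 50, forced guess).

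| True correct rate | P(pass) |
|---|---|
| 50% | 0.444 |
| 55% | 0.197 |
| 60% | 0.057 |
| 65% | 0.010 |
| 70% | 0.0009 |

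Clear unblinding is usually caught. Under a forced guess the fault is one-directional: the rule is too strict.

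**Step 3: don't-know allowed and counted as not correct** (assumed rates, n = 50). Under perfect blinding p = 0.5 × (1 − share answering don't-know).

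| Don't-know | p | P(fail), perfect blinding |
|---|---|---|
| 10% | 0.45 | 0.284 |
| 20% | 0.40 | 0.098 |
| 30% | 0.35 | 0.021 |

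The leniency shows when guessers are in fact informed. With 30% don't-know and 70% of guessers right, p = 0.7 × 0.7 = 0.49, and the rule passes with probability 0.500.

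**Step 4: guesses that lean to one arm without any unblinding** (25 per arm). False failure is 0.557 for a 60/40 lean, 0.571 for 80/20 and 0.595 for 90/10. With unequal realised arms it can move either way: if 80% guess IVF, it is 0.485 with 24 IVF and 26 control, and 0.728 with 27 IVF and 23 control.

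**Step 5: an example replacement.** Pass if the one-sided 95% Clopper-Pearson upper bound for the pooled correct rate is below 70%. At n = 50, 29 correct gives a bound of 0.699 (pass) and 30 gives 0.717 (fail), so the cutoff is 29.

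| True correct rate | P(X ≤ 29), n = 50 |
|---|---|
| 50% | 0.899 |
| 60% | 0.439 |
| 70% | 0.048 |

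With a 65% limit the cutoff is 26 and perfect blinding passes with probability 0.664; with a 75% limit it is 31 and 0.968.

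Fewer guessers weaken the rule. With the 70% limit:

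| Guessers | Cutoff | False failure, perfect blinding |
|---|---|---|
| 50 | 29 | 0.101 |
| 43 | 24 | 0.180 |
| 35 | 19 | 0.250 |
| 25 | 13 | 0.345 |

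**The case against.** The strongest objection is that the plan never says the guess is forced. Someone who answers don't-know has not correctly identified the arm, so on a literal reading such answers count towards success, and false failure drops to 28%, 10% or 2% at the rates in Step 3. This stands as a limit on the 50% to 56% figure, which holds only for a forced guess. It does not rescue the rule: the same sentence is then too easy to satisfy.

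Second, Aim 1b carries no stop/go consequence, and a reader who sees 26 of 50 correct will recognise a result near chance. That is fair, and it limits the harm to a wrong label on one feasibility result. But the aim does state a success threshold, and the plan offers the blinding check as an innovation.

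Third, any replacement involves judgement. The 70% limit comes from nowhere in the plan, and it passes a true 60% correct rate 44% of the time, against 5.7% under the current rule. It also loses power to confirm good blinding when few people guess. These costs are real and should be weighed when the limit is set.

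Fourth, because the question is asked after the infusion, a correct guess may reflect pain relief and not a failed cover. This applies equally to the current rule and to the replacement. It restricts what either can say about the cover, but it does not defend the threshold.

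**Conclusion.** The concern holds. The Aim 1b threshold equals the result expected from perfect blinding with two arms, with no allowance for sampling error. With independent, even, forced guesses, false failure is 55.6% if all 50 answer and 50% for any odd number. If don't-know is permitted and counted as not correct, the rule becomes lenient, to a degree that depends on how often that answer is given. Nothing else in the plan settles which case applies.

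A smaller gap sits beside it: the plan promises a verdict on assessor blinding, but Aim 1b covers participants only, so that verdict has no criterion.

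This should be fixed before the blinding data are interpreted. It bears on the feasibility conclusion and the claimed validation of the cover, and leaves the primary pain analysis untouched.

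**What to change.** Reword Aim 1b and add a short blinding analysis to III.C.6:

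1. State that 50% correct is expected under perfect blinding with a forced guess.
2. Fix the response options (IVF or control, with or without don't-know) and define the denominator as those who give a guess. Report don't-know and missing answers by arm.
3. Replace the present threshold with a pre-set tolerance above chance on the pooled correct rate. An example is success if the one-sided 95% exact upper bound is below 70%: at most 29 of 50, or at most 24 if 43 guess. The limit is for the sponsor to set.
4. Report guesses and Bang's index by arm with 95% confidence intervals as description only. A shared lean towards IVF would fail a per-arm rule without any unblinding: with a 70% lean and 25 per arm, the pooled cutoff of 29 passes with probability 0.918, but a per-arm index limit of 0.2 or 0.3 passes with probability only 0.189 or 0.323.
5. For outcome assessors, either state a criterion or say that the result is descriptive.
6. Acknowledge that guesses made after treatment may reflect pain relief.

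The cost is rewording and a fixed answer format, with no extra patients or visits. Besides the weaker detection of partial unblinding noted above, two limits remain. With 25 per arm, the 95% interval for Bang's index is about ±0.39 (1.96 × 2 × √(0.25/25) = 0.392). If one assessor rates several patients, those guesses are not independent.

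### Does predicting lower pain scores at follow-up oblige the plan to list a 48-hour pain outcome?

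*Combined protocol and SAP*

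**What the plan says.** Section II (Specific aims) states under Hypothesis 2 that "IVF administration will result in reduced pain scores in the ED and at follow-up". Its single aim concerns a gain of at least 1.3 points on the 0-10 scale "as compared to controls between time 0 and one hour". The Abstract puts the efficacy hypothesis at the same time point: "greater improvement in pain one hour after treatment as compared to controls".

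On measurement, the narrative in section II says that "pain, functional status, and side effects will be assessed at time zero, one hour, two hours and 48 hours". Section III.C.4 (Data collection) ties two instruments, a four-level categorical scale and a 0-10 verbal scale, to three times: "We will assess pain at time 0 (start of the intervention), one hour (end of the intervention), and two hours". For the contact two days after the patient leaves the ED, it adds: "During this follow up assessment we will ask participants about their current pain". Recurrence of pain is asked about as well. No scale is named there. The same call carries the global assessment, which asks "would you wish to receive the same IV fluid treatment again".

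Section III.C.5 (Outcomes) lists one primary and four secondary outcomes. Section III.C.6 (Analysis) describes an analysis for the primary outcome only. Aim 1c, under Hypothesis 1, covers the ability to "successfully obtain patient follow-up at one hour, two hours, and 48 hours in at least 85% of participants".

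**The concern.** A hypothesis should be matched by an outcome that can test it. Here the follow-up half of Hypothesis 2 has no aim, no listed pain outcome and no named instrument. The one listed outcome collected at the 48-hour call is the global assessment, which measures willingness to be treated the same way again and not pain.

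Two things could be at stake. A 0-10 rating that is not asked for at the call cannot be recovered later. And with both current pain and recurrence left undefined, the measure used to judge the follow-up prediction could be chosen after the data are seen.

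**Working it through.** **1. Match each listed outcome to a time (III.C.5).**

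| Outcome | Pain? | Time |
|---|---|---|
| Change in 0-10 rating (primary) | yes | one hour |
| Pain-free | yes | two hours |
| Change in verbal scale | yes | two hours |
| Global assessment | no | 48-hour call |
| Functional disability | no | one and two hours |

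Five outcomes, of which three concern pain: one at one hour, two at two hours, none at 48 hours. The mismatch with the wording of Hypothesis 2 is confirmed.

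**2. Could follow-up mean two hours?** Aim 1c uses the word for one, two and 48 hours alike. On that usage the two-hour change in the verbal scale would partly carry the prediction. This is the weaker reading. Hypothesis 2 sets follow-up against time in the ED, and section IV (Expected outcome) uses the word for assessments after discharge. The post-ED reading is the natural one.

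**3. Is the scale really open?** Section II puts 48 hours in the same series as time zero, one hour and two hours and gives no hint of a different measure. Of the two scales in III.C.4, one is described as verbal, which suits a telephone call. The plan is silent on the scale at 48 hours, but the inference is short.

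**4. Does the sample size depend on it?** III.C.6 bases 50 patients on estimating 85% adherence to within 10 percentage points at 95% confidence:

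- n = 1.96² × 0.85 × 0.15 / 0.10² = 48.98, rounded up to 49, which agrees with the stated 50.
- Half-width at n = 50: 1.96 × √(0.85 × 0.15 / 50) = 0.099, or 9.9 percentage points.

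No pain outcome enters this calculation.

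**5. What would a listed 48-hour comparison show?** The Aim 1c target gives 0.85 × 50 = 42.5, so at least 43 people reached, or 21.5 per arm on average. The documents give no SD for the 0-10 score, so a range is assumed. The 95% half-width for the difference between arms is 1.96 × SD × √(2 / 21.5):

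| Assumed SD | Half-width (points) |
|---|---|
| 2 | 1.20 |
| 2.5 | 1.49 |
| 3 | 1.79 |
| 3.5 | 2.09 |

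Except at the smallest assumed SD, the half-width exceeds the 1.3 points that III.C.5 gives as the minimum clinically significant difference between groups. The comparison would be descriptive whether it is listed or not.

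**The case for a change.** The strongest case for a change is that the choice of scale is made at data capture and cannot be repaired at analysis. Section I gives the pilot's purpose as both feasibility and preliminary outcome data, so a pain answer recorded in an undefined form serves the second purpose poorly. The remedy is also cheap: name the scale and list one exploratory comparison, or drop three words from the hypothesis.

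Part of this stands. The scale at the call is not named, recurrence is not defined, and the 48 hours runs from leaving the ED in III.C.4 but sits in a series starting at time zero in section II. A careful author would have tidied these points.

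It does not stand as a reason to amend the plan. No stated rule or number gives a wrong result. Naming the scale would write down what the rest of the text already suggests. Even if the categorical scale were used instead, the answer would be an ordinal pain measure that the plan already employs. Deleting the words would change no data and no analysis. The scope for choosing a measure afterwards is limited in effect, because a 48-hour pain result is outside the listed outcomes and could be offered only as exploratory.

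**Conclusion.** No change follows. Hypothesis 2 is worded more broadly than its aim, the Abstract and the outcome list, and the follow-up half lacks a listed pain outcome. This is missing detail that analysts would fill sensibly. The primary outcome at one hour, the 50-patient sample size and the feasibility aims, including 48-hour follow-up in Aim 1c, are untouched. Section IV leaves the efficacy question to a larger, adequately powered trial.

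The conclusion rests on two assumptions: that the verbal 0-10 rating is the one asked for at the call, and that any 48-hour pain comparison is reported as exploratory with the number reached in each arm. The interval widths rest further on the assumed SD of 2 to 3.5 points and on follow-up at the 85% target.
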